CV	Coefficient of variation
CYP	Cytochrome
DSMB	Data safety monitoring board
ECHO	Echocardiogram
ECMO	Extracorporeal membrane oxygenation
EC	Ethics Committee
eCRF	Electronic case report form
EMA	European Medicines Agency
ERA	Endothelin receptor antagonist
°F	Fahrenheit
FDA	Food and Drug Administration
FiO ₂	Fraction of inspired oxygen
GCP	Good Clinical Practice
HCO ₃	Bicarbonate
HR	Heart rate
ICH	International Conference on Harmonisation
ICU	Intensive care unit
IND	Investigational new drug
iNO	Inhaled nitric oxide
IRB	Institutional Review Board
IV	Intravenous
IWRS	Interactive web response system
kg	Kilogram
LFTs	Liver function tests
MAP	Mean airway pressure
MAS	Meconium aspiration syndrome

min	Minute
mg	Milligram
mmHg	Millimeters mercury
mL	Milliliter
n	Number
ng	Nanogram
NICU	Neonatal intensive-care unit
NO-cGMP	Nitric oxide cyclic guanosine monophosphate
NT-proBNP	N-terminal pro-Brain Natriuretic Peptide
OI	Oxygenation index
P/F	Ratio of arterial oxygen concentration to the fraction of inspired oxygen (PaO ₂ /FiO ₂)
PA	Pulmonary artery
PaCO ₂	Partial pressure of arterial carbon dioxide
PAH	Pulmonary arterial hypertension
PaO ₂	Partial pressure of arterial oxygen
PCVC	Percutaneous central venous catheter
PDA	Patent ductus arteriosus
PDE-5i	Phosphodiesterase type-5 inhibitor
PFO	Patent foramen ovale
PGI ₂	Prostacyclin
PH	Pulmonary hypertension
PICC	Peripherally inserted central catheter
PK	Pharmacokinetic
PPHN	Persistent pulmonary hypertension of the newborn
PR	Pulmonary regurgitation
PvCO ₂	Partial pressure of venous carbon dioxide
PvO ₂	Partial pressure of venous oxygen
RDS	Respiratory distress syndrome
RR	Respiratory rate
RV	Right ventricle
SAE	Serious adverse event
SC	Subcutaneous
SD	Standard deviation
SpO ₂	Saturation of peripheral oxygen
SvO ₂	Mixed venous oxygen saturation
Temp	Temperature
TR	Tricuspid regurgitation
US	United States
UVC	Umbilical venous catheter
VBG	Venous blood gas
VSD	Ventricular septal defect
µL	Microliter

1 BACKGROUND AND RATIONALE

1.1 DEFINITION OF CLINICAL PROBLEM

As part of the normal birth transition, the pulmonary vascular resistance decreases as the lungs expand and the ductus arteriosus closes. Persistent pulmonary hypertension of the newborn (PPHN) is the failure of the pulmonary vasculature to make this transition leading to diminished cardiac output and obligatory right to left shunting. The incidence of PPHN has been estimated at 1.9/1000 live births with reported mortality ranging from 4-33% (1). PPHN can be characterized as one of three types: abnormally constricted pulmonary vasculature due to lung parenchymal diseases (e.g., meconium aspiration syndrome [MAS], respiratory distress syndrome [RDS] or pneumonia); normal lung parenchyma with remodeled pulmonary vasculature (idiopathic PPHN) or hypoplastic vasculature as seen in congenital diaphragmatic hernia [CDH]) (2).

Management of PPHN is aimed at optimization of cardiac and lung function and reducing pulmonary vascular resistance. This may include: mechanical ventilation, sedation, neuromuscular blockade, inotropic support, intravenous volume replacement, pulmonary vasodilator therapy, inhaled nitric oxide, or therapy with phosphodiesterase-5 inhibitors (PDE-5i) or endothelial receptor antagonists (ERA), and in severe cases, mechanical support with extracorporeal membrane oxygenation (ECMO).

Currently, inhaled nitric oxide (iNO) is the only treatment for PPHN approved by the US Food and Drug Administration (FDA) and European Medicines Agency (EMA). Inhaled nitric oxide was studied in two double-blind, placebo-controlled trials which enrolled neonates with hypoxic respiratory failure. The objectives of these studies were to determine whether iNO would reduce the occurrence of death and/or initiation of ECMO in neonates with hypoxic respiratory failure. In these trials, hypoxic respiratory failure was caused by MAS, pneumonia/sepsis, idiopathic PPHN, and RDS. Both studies demonstrated that iNO reduced the need for ECMO in this population; however there was no difference in mortality in either study. Neither of these trials included subjects with CDH. Across these studies, approximately 30-40% of neonates did not respond to iNO (defined as a change from baseline in partial pressure of oxygen in arterial blood (PaO₂) of ≤ 10 mmHg) (3,4). In clinical

practice, critically ill neonates unresponsive to iNO will typically receive ECMO; however, an alternative option could include the addition of another pulmonary vasodilator in an effort to reduce the pulmonary vascular resistance.

1.2 REMODULIN (TREPROSTINIL) BACKGROUND

Treprostinil is a chemically stable tricyclic analogue of prostacyclin (PGI₂), which is approved for the treatment of pulmonary arterial hypertension (PAH) in the US, EU, and many other countries under the brand name Remodulin. The pharmacology of treprostinil has been extensively characterized for the treatment of PAH using either a subcutaneous (SC) or intravenous (IV) continuous infusion. A detailed description of preclinical and clinical information of treprostinil for injection is provided in the Investigator's Brochure.

The major pharmacological actions of treprostinil are direct vasodilatation of pulmonary and systemic arterial vascular beds and inhibition of platelet aggregation. *In vitro*, treprostinil induced concentration dependent relaxation of rabbit isolated precontracted mesenteric arteries, inhibition of adenosine diphosphate (ADP), induced aggregation in human platelet rich plasma, and inhibition of ADP induced platelet aggregation in rat platelet rich plasma. In animals, the vasodilatory effects of treprostinil reduce right and left ventricular afterload, increasing cardiac output and stroke volume. Prostacyclins lower pulmonary artery pressure, increase cardiac output without affecting the heart rate, improve systemic oxygen transport as well as possibly reversing pulmonary arterial remodeling. There is also increasing evidence that the ability to block the proliferation of pulmonary artery smooth muscle cells may contribute, along with the capacity to produce vasodilatation and inhibition of platelet aggregation, to the therapeutic effects of prostacyclins in the treatment of PAH. The mechanism of action is therefore likely to be multifactorial.

The efficacy of Remodulin in adult patients with PAH has been established in both the IV and SC routes (5-7). However, there is a growing body of literature to support the use of Remodulin in the pediatric population. Multiple published reports of the use of chronic Remodulin in children as young as 20 weeks of age have been reported without unexpected adverse events (AEs) (8-10). Acute dosing of SC and IV Remodulin has been used in children as young as 6-8 weeks, including a case report published regarding the use of IV

Remodulin in a neonate for the treatment of PPHN (11-13). In this case study, the subject was initiated at a dose of 1ng/kg/min of IV Remodulin and was titrated to a dose of 4ng/kg/min. Clinical response was noted within four days of initiation and down titration began after 10 days on therapy (11).

In children and adults, the most frequent AEs reported with Remodulin were related to the known pharmacological properties of treprostinil. These prostacyclin-related AEs are typically due to systemic effects that are characteristic of the prostacyclin class of medications (e.g., diarrhea, headache, nausea). To date, well over 10,000 patients, which includes over 1,000 pediatric patients (<12 years of age) and study subjects have been exposed to Remodulin for more than 11 years.

1.3 RATIONALE FOR DEVELOPMENT OF STUDY DRUG IN DISEASE / CONDITION

The pathophysiology of PPHN includes disruptions in the nitric oxide cyclic guanosine monophosphate (NO-cGMP), prostacyclin-cyclic adenosine monophosphate (cAMP), and endothelin signaling pathways. Prostacyclin appears to increase during late gestation suggesting its importance in the cardiopulmonary transition of newborns. An imbalance in the biosynthesis of prostacyclin and synthesis of the constrictor thromboxane A₂ has been identified to occur in pulmonary arterial hypertension, and similar imbalances in vasoactive and vasoconstrictive mediators has been observed in studies of fetal pulmonary hypertension (14,15). Current standard of care treatment for PPHN is iNO; however, approximately 40% of patients do not fully respond to iNO (2,3). Treprostinil, a prostacyclin analogue, may work in synergy with iNO for the treatment of PPHN to enhance smooth muscle relaxation of the pulmonary vasculature. Treprostinil may also decrease the inflammatory response and improve pulmonary vascular remodeling in these patients.

1.4 CLINICAL HYPOTHESIS

This study aims to assess the safety and treatment effect of IV Remodulin as add-on therapy in neonatal subjects with PPHN as compared to placebo. This study will enroll subjects with PPHN who do not show an adequate response to iNO (defined as an oxygenation index [OI] of 15 or greater after three hours of iNO therapy) with the hypothesis that the addition of

Remodulin will reduce the rate of clinical worsening defined as death, the need for ECMO, or the need for additional pulmonary vasodilator therapy as compared to placebo. Additionally, this study aims to evaluate the dosing and pharmacokinetics of Remodulin in the neonatal population.

2 OBJECTIVES

2.1 PRIMARY OBJECTIVE

To explore the safety and treatment effect of IV Remodulin as add on therapy in neonates with PPHN compared to placebo. Efficacy will be assessed by a composite endpoint of clinical worsening through Day 14 as defined by one of the following:

- Death
- Initiation of ECMO per institutional policies
- Need for additional treatment (initiation of an additional targeted pulmonary vasodilator therapy [e.g., phosphodiesterase-5 inhibitor [PDE-5i], endothelin receptor antagonist [ERA], prostanoid, L-citrulline]; refer to Section 3.3.1.1.1).

2.2 SECONDARY OBJECTIVES

To assess the effect of IV Remodulin as add on therapy in neonates with PPHN compared to placebo in the following:

- Change in OI from Baseline to Hours 12, 24, 72, Days 7 and 14 and/or prior to study drug discontinuation/weaning
- Change in PaO₂ /FiO₂ (P/F ratio) from Baseline to Hours 12, 24, 72
- Change in pre and post-ductal oxygen saturation (SpO₂) from Baseline to Hours 6, 12, 24 and 72
- Time to discontinuation of iNO
- Time on mechanical ventilation
- Time to initiation of ECMO
- Time to clinical worsening
- Change in N-terminal pro-Brain Naturetic Peptide (NT-proBNP)
- Safety (AEs, clinical laboratories, and physical examination findings)

[figure not shown]
To evaluate treprostinil pharmacokinetics in neonates with PPHN.

3 EXPERIMENTAL PLAN**3.1 STUDY DESIGN**

This is a randomized, double-blind, placebo-controlled, multi-center, comparative study that will enroll neonates in the intensive care unit (ICU) with PPHN. Eligible subjects must have two consecutive OIs of 15 or greater, separated by at least 30 minutes, after having received iNO for at least 3 hours. Once enrolled, subjects will be randomized to receive Remodulin (treprostinil) or placebo.

This study is designed to evaluate the treatment effect of Remodulin as add-on therapy compared to placebo during a 14-day treatment period. However, to assess continued safety in this neonatal population, subjects with residual or chronic pulmonary hypertension that does not fully resolve within 14 days may continue to receive study drug for up to an additional 14 days (up to 28 days total) per the Investigator's discretion. Post-treatment data will be collected until death, time of hospital discharge, time of withdrawal from study, or for 4 weeks after last dose of study drug, whichever comes first. Subjects with ongoing AEs at the time of hospital discharge will continue to be followed for their AEs until either resolution (or return to normal or Baseline values), until judged by the Investigator to no longer be clinically significant, or until 4 weeks after last dose of study drug. All SAEs should be followed until resolution, death, or the subject is lost to follow-up, even if they are ongoing more than 4 weeks after last dose of study drug.

Figure 3-1 Design Schematic

3.2 OVERALL SCHEDULE OF TIMES AND EVENTS

No procedures specifically for purposes of this study should be performed before a parent or legal guardian has provided written informed consent. All study-related events and activities including specific instructions, procedures, concomitant medications, and descriptions of AEs should be recorded in the appropriate source documents and electronic case report forms (eCRFs). [Table 3-1](#) displays the overall schedule of events.

Table 3-1 Schedule of Events

Procedures	Screening	Study Drug Initiation and Administration					Study Drug Discontinuation				Follow-up/Final Assessments
		Baseline ^a	First 72 hours of treatment	Day 4 throughout duration of study drug treatment ^b	Day 7 and Day 14 ^b	Dose Changes	Immediately Prior to Study Drug Weaning or Discontinuation ^k	Every 24 hrs While Weaning ^p	Study Drug Discontinuation (within 12 hours) ^q	48 hrs after Study Drug Discontinuation ^q	
Informed Consent	X										
Inclusion/Exclusion Criteria	X										
Randomization		X									
Maternal History	X										
Physical Examination	X	X	X(daily)		X ^b		X ^k	X	X		X
Vital Signs ^d	X	X	X ^{d,o} (q6 hrs)	X ^b (daily)	X ^b	X ^d	X ^k	X	X	X	X
OI Assessment ^e	X	X	X ^{e,o} (q6 hrs)	X ^{b,e} (daily)	X ^{b,e}		X ^{e,k}				
FiO ₂	X	X	X ^o (q6 hrs)	X ^b (daily)	X	X	X ^k	X	X		
Mean Airway Pressure ^f	X	X	X ^{e,o} (q6 hrs)	X ^{b,e} (daily)	X		X ^{e,k}	X	X ^e		
Blood Gas/Lactate ^g	X	X	X ^{e,o} (q6 hrs)	X ^{b,e} (daily)	X ^b		X ^{e,k}		X ^e		
Clinical Laboratories ^h		X			X ^b		X ^k		X	X	X
NT-proBNP		X	X(daily)		X ^b		X ^k		X		
Echocardiogram ⁱ	X				X ^b		X ^k			X	
Clinical Worsening ^j		X---	---X---	---X(through Day 14)	X						
Pharmacokinetic Sample collection			X ^l (collected after 24 hrs of treatment)				X ^k				
Concomitant Medications ^m	X	X---	---X---	---X---		---X---	---X---	---X---	---X---	---X	
Record Doses of Inotropes/		X				X	X	X	X	X	
Adverse Events ⁿ	X	X---	---X---	---X---		---X---	---X ⁿ ---	---X---	---X---	---X---	---X ⁿ

^aScreening assessments can be used as Baseline values if they are conducted within 3 hours of randomization. Length and weight will only be assessed at Baseline. All doses of study drug will be calculated using Baseline weight. Study drug initiation is Hour 0 on the first day of treatment.

^bThe Day 4 and the 72 hour time point assessment will fall on the same calendar day. A separate set of assessments should be captured for the Day 4 assessment. Day 7 and Day 14 assessments should be performed even if the subject has discontinued study drug. If subjects are discharged from the hospital prior to study Day 14, Day 14 assessments should be completed prior to hospital discharge. Subjects may receive up to 28 days of study drug.

^cHospital discharge or 4 weeks after discontinuation of study drug (whichever comes first).

^dVital signs include BP, HR, RR, temperature, and SpO₂. SpO₂ will be collected both pre- and post-ductal for the first 72 hours. BP, HR, and SpO₂ will be collected with each study drug dose change.

^eOI will be calculated as long as the subject is on mechanical ventilation and arterial blood gasses (ABGs) are collected.

^fCollected for as long as the subject is on mechanical ventilation.

^gABGs will be collected as long as the subject has arterial access. Venous or capillary blood gas will be collected thereafter. Lactate will be drawn with each blood gas.

^hClinical labs include: chemistries, hematology, and liver function tests. Performed by institutional laboratory.

ⁱIf subject had historic ECHO performed within 36 hours prior to time informed consent was signed, then ECHO does not need to be repeated at Screening. A ±2 day window for Day 7 and Day 14 ECHO.

^jClinical worsening is assessed from Baseline to the conclusion of Day 14 or hospital discharge, whichever comes first. Events occurring after Day 14 will not count towards the primary analysis of clinical worsening.

^k“Prior to wean” assessments will be collected after the dose has been maintained for at least 12 hours and no more than 1 hour prior to beginning to wean study drug. Assessments should be collected for subjects randomized to placebo; PK sample not required in subjects randomized to placebo. In the event that the subject will continue to receive Remodulin beyond Day 28, prior to wean assessments should take place on Day 28.

^lA single PK sample will be collected after 24+6 hours of study drug dosing. The dose should have been maintained for at least 2 hours prior to the sample collection time.

^mConcomitant medications will be captured up to 48 hours after the subject has stopped receiving study drug.

ⁿDocumentation of AEs will be recorded from the time informed consent is provided until subject is withdrawn from study, time of hospital discharge, or for 4 weeks after last dose of study drug, whichever comes first. All SAEs should be followed until resolution, death, or the subject is lost to follow-up, even if they are ongoing more than 4 weeks after completion of the subject’s last dose of study drug/final visit. If the subject receives Remodulin after hospital discharge, beyond Day 56/End of study, or following withdrawal from the study, AEs/SAEs will be subject to AE/SAE reporting under local government post-marketing AE/SAE reporting requirements.

^oApproximately every 6 hours (± 2 hours).

^pNot required for subjects unblinded and identified on placebo, or subjects continuing on Remodulin beyond Day 28.

^qIn the event that study drug is not discontinued (i.e., the subject continues on Remodulin beyond Day 28), the “Study Drug Discontinuation” and “48 Hour after Study Drug Discontinuation” assessments will not be collected. Follow-up/End of Study assessments will be performed.

3.3 CLINICAL ASSESSMENTS

3.3.1 *Efficacy*

3.3.1.1 *Assessment of Clinical Worsening*

Efficacy will be assessed by a composite primary endpoint of clinical worsening assessed at Day 14 or hospital discharge, whichever comes first, as defined by one of the following events:

- Death
- Initiation of ECMO per institutional policies
- Need for additional treatment (initiation of additional targeted pulmonary vasodilator therapy for PPHN)

Clinical worsening will be evaluated from Baseline (initiation of study drug) to the time of discontinuation of study drug, discharge from the hospital, or at the conclusion of Day 14, whichever comes first. Events occurring after the first 14 days of treatment will not count towards the primary endpoint.

3.3.1.1.1 *Need for Additional Treatment*

The following criteria should be met prior to initiation of additional targeted pulmonary vasodilator therapy for PPHN (all criteria required):

- OI measurement >20
- In the clinical judgment of the Investigator, subject requires addition of another targeted pulmonary vasodilator therapy (e.g., PDE-5i, ERA, alternate prostanoid [epoprostenol, iloprost], L-citrulline) due to worsening of clinical status or unsatisfactory clinical response
- Subject has received study drug for at least 24 hours and reached a minimum dose of 10ng/kg/min, or is unable to tolerate further increases (e.g., due to systemic hypotension); **OR**
 - If less than 24 hours, subject has two consecutive OI measurements >30 separated by at least one hour **OR** two consecutive arterial lactate levels of $\geq 4\text{mmol/L}$ separated by at least one hour

If an additional pulmonary vasodilator therapy is added after Day 14, the subject will not meet the primary endpoint definition of clinical worsening.

3.3.1.1.2 *Extracorporeal Mechanical Oxygenation (ECMO)*

ECMO will be initiated per institutional policy. Any subject who initiates on ECMO during the first 14 days of the study will meet the definition of clinical worsening. The initiation of ECMO after Day 14 will not be considered a clinical worsening event for the purposes of the primary endpoint of the study.

3.3.1.1.3 *Death*

Any subject who dies within the first 14 days of the study will meet the definition of clinical worsening. Deaths that occur after Day 14 will not be considered a clinical worsening event for the purposes of the primary endpoint of the study.

All deaths will be reported as a serious adverse event (SAE) (Section 9).

3.3.1.2 *Oxygenation Index (OI)*

The OI is an assessment of how much oxygen diffuses across the membranes of the lungs and into the blood when a subject inhales. Higher OIs indicate an increased risk of poor subject outcomes because the subject is unable to get as much oxygen out of each breath. Typically when the OI is greater than 40, ECMO is considered. The OI is calculated as follows:

$$OI = [MAP(\text{mmHg}) \times \text{FiO}_2(\%) / \text{PaO}_2(\text{mmHg})] \times 100$$

An OI will be calculated at Screening, Baseline, approximately every 6 hours for the first 72 hours, daily starting on the fourth day of study drug for as long as the subject is on study drug, and within 1 hour prior to weaning study drug for as long as the subject has arterial access for collection of arterial blood gases (ABGs) and is on mechanical ventilation (Table 3-1). An OI will be collected on study Day 7 and Day 14 (as long as the subject has arterial access for collection of ABGs and is on mechanical ventilation) regardless if the subject has already been weaned from study drug.

The OI should be used to guide study drug dosing. When the OI cannot be calculated (i.e., no arterial access for ABGs and/or subject not on mechanical ventilation), FiO_2 will be used to guide dosing (per Section 6.1.3).

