4.3 PRESCRIBED THERAPY

4.3.1 *Concomitant Medications*

All subjects will be concurrently receiving iNO prior to randomization. Subjects should be adequately treated (as determined by the Investigator) with standard of care treatments for PPHN (e.g., inotropes, opioids, sedation) prior to enrollment and during the study. Doses of medications should be adjusted as needed during the study. All concomitant medications will be recorded in the subject's eCRF up until 48 hours after discontinuation of study drug. Any concomitant medications used in the treatment of an AE or SAE will be recorded even if it occurs more than 48 hours after discontinuation of study drug.

Caution should be used with cytochrome P450 (CYP) 2C8 enzyme inducers/inhibitors, such as rifampin or gemfibrozil, as plasma concentrations of treprostinil may be altered. Concomitant administration of Remodulin with diuretics, antihypertensive agents or other vasodilators may increase the risk of symptomatic hypotension. Remodulin inhibits platelet aggregation, there may be an increased risk of bleeding when administered with other anticoagulants, such as warfarin, heparin, or NSAIDs.

4.3.1.1 *Inotropic Dose Changes*

Doses of inotropic and vasoactive agents (e.g., dopamine, epinephrine, dobutamine, milrinone, vasopressin, norepinephrine) will be recorded with each dose change of study drug.

4.3.1.2 *Initiation of a Pulmonary Vasodilator Therapy*

If the Investigator initiates a targeted pulmonary vasodilator (after meeting the requirements outlined in Section 3.3.1.1.1) during the first 14 days after randomization, the subject will meet the definition of the primary endpoint of clinical worsening.

Subjects randomized to study drug who meet the definition of clinical worsening may continue to receive study drug for a total of up to 28 days at the discretion of the Investigator.

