6.1.3 Dose Initiation and Titration

The starting dose of study drug is 1ng/kg/min, which is not anticipated to provide clinical effects. The dose of study drug should be increased by up to 2ng/kg/min every 2 hours, as tolerated and clinically indicated by the physician, based upon the OI; when the OI is no longer calculable, the FiO₂ will be used to guide dosing. As some subcutaneous infusion pumps may not accommodate a starting dose of exactly 1ng/kg/min, the site may proceed with a starting dose as close to 1ng/kg/min as possible. The initial starting dose should not exceed 2ng/kg/min and should be increased by approximately 1-2ng/kg/min every 2 hours as tolerated and clinically indicated by the

physician. Subject response to study drug is individualized; not all subjects will tolerate the same rate of titration and clinically beneficial doses will vary. There is no maximum dose limit. Titration will be made per the subject's response in clinical symptoms.

If the OI is 15 or greater, the dose of study drug should be increased in the absence of dose-limiting adverse events (e.g., hypotension). If the OI is between 10 -14 and the study drug dose is ≤ 10 ng/kg/min, the dose should continue to be increased, as tolerated. If the study drug dose is >10 ng/kg/min and the OI is between 10 -14, any further dose escalation will be left to the discretion of the clinicians/Investigators according to the clinical condition of the subject, and the perceived need for additional pulmonary vasodilation. Once the OI is <10 and iNO has been discontinued, study drug weaning can begin (Section 6.1.4).

If the OI cannot be calculated, dose adjustments will be based upon FiO₂. The study drug dose should be increased when the FiO₂ is $\geq 60\%$ in the absence of dose-limiting adverse events (e.g., hypotension). Once the FiO₂ is $<60\%$ and iNO has been discontinued, weaning of study drug can begin. Table 6-1 below describes the suggested dose titration parameters.

Table 6-1 Suggested Study Drug Dose Titration Parameters

Oxygenation Index	FiO ₂ (To be used when OI is not calculable)	Dosing Strategy
≥ 15	$\geq 60\%$	Dose increase, as tolerated
10-14 (dose >10 ng/kg/min)	--	Hold dose or dose increase if clinical condition warrants further pulmonary vasodilation.
10-14 (dose ≤ 10 ng/kg/min)	--	Dose increase, as tolerated
<10	$<60\%$	Begin weaning. The iNO should be weaned and discontinued prior to initiating weaning of study drug.

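### Protocol 3.3.1.1 has one sentence that closes the primary-endpoint window when study drug stops; every other statement of the window in the Protocol and SAP leaves it open

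*Protocol*

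**What the plan says.** Protocol 3.3.1.1 defines the window twice. Its opening line has "clinical worsening assessed at Day 14 or hospital discharge, whichever comes first". After the component list it says "Clinical worsening will be evaluated from Baseline (initiation of study drug) to the time of discontinuation of study drug, discharge from the hospital" or the end of Day 14, whichever is earliest.

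The component rules that follow carry no drug-stop limit:

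- ECMO (3.3.1.1.2): "Any subject who initiates on ECMO during the first 14 days of the study will meet the definition of clinical worsening".
- Death (3.3.1.1.3): "Any subject who dies within the first 14 days of the study will meet the definition of clinical worsening".
- Added vasodilator (4.3.1.2): a qualifying start counts if it falls "during the first 14 days after randomization, the subject will meet the definition of the primary endpoint of clinical worsening".

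Table 3-1 footnote j and Protocol 10.3.1 run the window to Day 14 or discharge. The synopsis, Protocol 2.1, SAP 2.1 and SAP 10.1.1.2 run it through Day 14. SAP Table 8-1 runs from Baseline to Day 14 and censors at the last assessment or 14 days, not at the last dose. Footnote b adds that "Day 7 and Day 14 assessments should be performed even if the subject has discontinued study drug", and the Day 7 and Day 14 list in 7.3.2.1 includes assessing clinical worsening.

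**The concern.** Stopping study drug happens after randomisation and treatment can affect it, through tolerability, response or weaning. An endpoint window that closes at that moment can have a different length in each arm, which does not fit the planned intention-to-treat comparison.

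The SAP would not repair the damage. SAP 10.2.5 takes worsening status from the clinical worsening page of the eCRF. A site that follows the sentence could enter No for an infant who worsens after stopping drug but before Day 14. SAP 8.3.1 converts only missing values to Yes, so a recorded No stays.

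With 33 infants per arm, single events can decide the result, and the primary test gates both the secondary tests (SAP 8.4) and the sensitivity analyses (SAP 10.1.1.3).

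**Working it through.** **1. Statements of the window side by side**

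| Place | Ends at drug stop? | Ends at discharge? |
|---|---|---|
| Protocol 3.3.1.1, second statement | Yes | Yes |
| Protocol 3.3.1.1, opening line | No | Yes |
| Table 3-1 footnote j; Protocol 10.3.1 | No | Yes |
| Protocol 3.3.1.1.2, 3.3.1.1.3, 4.3.1.2 | No | No |
| Synopsis; Protocol 2.1 | No | No |
| SAP 2.1, 10.1.1.2, Table 8-1 | No | No |

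Take an infant whose drug stops on Day 8 and who dies in hospital on Day 10. Under the challenged sentence this is not an event; under 3.3.1.1.3 it is. The table also shows a second disagreement, on whether discharge closes the window.

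**2. Which components could be lost**

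- Death: reported as an SAE, and Table 8-1 uses the death date. Largely recoverable.
- ECMO: start time is recorded in follow-up (synopsis). Largely recoverable.
- Added vasodilator: most exposed. Footnote m and 4.3.1 stop routine medication capture 48 hours after drug stop. There are two partial safeguards. First, "Any concomitant medications used in the treatment of an AE or SAE will be recorded even if it occurs more than 48 hours" after drug stop, although under 9.1.5 a non-serious disease-related event need not become an AE. Second, the Day 7 and Day 14 visits record medications even after weaning, although the 48-hour limit conflicts with that list.

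**3. The plan's own figure**

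Inputs (Protocol 10.2, SAP 5): 60% against 30%, one-sided 0.05, 80% power. With the pooled-variance formula and no continuity correction,

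n = [1.645 × √(2 × 0.45 × 0.55) + 0.842 × √(0.6 × 0.4 + 0.3 × 0.7)]² / 0.30² = 32.9, so 33 per arm.

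Power at 33 per arm is 80.1%, so the stated 66 reproduces. Correcting the window leaves this unchanged.

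**4. Size if events are lost (assumed inputs)**

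Let s be the vasodilator-only share of events and f the fraction of those uncounted. Observed rate = true rate × (1 − s × f). I enumerated two binomials exactly with n = 33 per arm and a Pearson chi-square without continuity correction. A win is a significant result with the lower rate on Remodulin.

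For s = 1/3:

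- f = 10%: 1/3 × 0.10 = 3.3% of events lost; 33 × 0.6 × 0.033 = 0.66 events in an arm with a 60% rate.
- f = 20%: 1/3 × 0.20 = 6.7% lost; 33 × 0.6 × 0.067 = 1.32 events.

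| Scenario | No loss | f = 10% | f = 20% |
|---|---|---|---|
| False win, 60% in both arms, equal loss (two-sided 0.05) | 3.0% | 3.0% | 3.1% |
| False win, Remodulin-only loss | 3.0% | 4.3% | 6.1% |
| False win, placebo-only loss | 3.0% | 2.0% | 1.4% |
| Power, 60% vs 30%, equal loss (two-sided 0.05) | 73.6% | 70.8% | 67.8% |
| Power, placebo-only loss | 73.6% | 67.7% | 61.4% |
| Power, Remodulin-only loss | 73.6% | 76.4% | 79.0% |
| Power, equal loss (one-sided 0.05) | 81.2% | 78.9% | 76.5% |

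The false-win rows count significant results in favour of Remodulin only, so their nominal level is 2.5%.

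Range from s = 1/6 with f = 10% (1.7% of events lost) to s = 1/2 with f = 20% (10% lost), two-sided: false win under Remodulin-only loss 3.6% to 8.4%; power under equal loss 72.2% to 64.8%; power under placebo-only loss 70.7% to 54.7%.

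**5. How much one event matters**

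20/33 against 12/33 gives z = (8/33) / √(0.485 × 0.515 × 2/33) = 1.97, significant at two-sided 0.05. Remove one placebo event: 19/33 against 12/33 gives z = 1.73, not significant.

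**The case against.** The strongest reply is that the analysis rule is settled elsewhere. Protocol 10.3.1 and the SAP count events without regard to drug status, the component rules say any subject, and worsening is assessed at Day 7 and Day 14 after weaning. A site would have to prefer one sentence to all of these. The eCRF page and its completion rules are not in the documents, so a wrong entry is possible but not shown.

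The exposed group is also small. For planned weaning, "Once the OI is <10 and iNO has been discontinued, study drug weaning can begin" (or FiO₂ below 60% when OI is not calculated), whereas a qualifying vasodilator start needs OI above 20 plus conditions on time on drug and dose, tolerance or early severity. OI is calculated only with mechanical ventilation and arterial gases. Drug is normally weaned, and the weaning period lies inside even the challenged window. Drug stopped after worsening follows an event already counted.

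Finally, the inflated false-win figures need loss in one arm only; equal loss leaves the false-win rate almost unchanged.

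All of this stands as a limit on size. It does not reconcile the text. Relapse after weaning and stops for other reasons (Protocol 8.1) remain, and the Protocol itself warns of rebound pulmonary hypertension on abrupt cessation. The phrases in 3.3.1.1 and 7.3.2 that refer to days of treatment or duration of therapy do not clearly set a second on-drug window.

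**Conclusion.** The concern holds and should be fixed. Confidence is high that the sentence contradicts every other statement of the primary-endpoint window, and low to moderate for the sizes. Those rest on an assumed vasodilator-only share and an assumed uncounted fraction, since the documents give neither.

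On the central assumptions the loss is about one event per arm or less. With equal loss it costs 2.8 or 5.8 points of two-sided power (73.6 − 70.8; 73.6 − 67.8), or 2.3 or 4.7 points at the one-sided level used for sample size (81.2 − 78.9; 81.2 − 76.5). The direction of any bias cannot be stated: unequal loss could favour either arm, and no arm-specific stop rates are given. The low starting point of 73.6% reflects the two-sided test, a separate matter from the window.

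**What to change.** - In Protocol 3.3.1.1, delete drug discontinuation from the list of events that end the window.
- In SAP 2.1 and Table 8-1, state that death, ECMO and added targeted vasodilator therapy count regardless of study drug status.
- Choose between through Day 14 and Day 14 or discharge, and use that one wording throughout both documents.
- Amend Table 3-1 footnote m and Protocol 4.3.1 so that targeted pulmonary vasodilator starts are recorded to the end of the window after drug stop, in line with the Day 7 and Day 14 list in 7.3.2.1.

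The cost is a few lines of text and slightly more data capture in infants who stop drug early. Worsening and medication items at Day 7 and Day 14 after drug stop are already required. Sample size, dosing and clinical criteria do not change.
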